9.12 Eighteen-month Follow-up ± 30 Days (Clinic Visit)

All subjects will complete a clinical assessment at 18 months (± 30 days) post-procedure with an in-person clinical visit to complete the Primary Endpoint Assessment. The 18-month follow-up visit will include the following assessments:

- Neurological assessment may be performed by a non-delegated neurology professional (e.g., board-certified or board-eligible neurologist, neurology fellow, neurology physician assistant, or neurology nurse practitioner, or NIHSS- and/or mRS-certified staff where applicable), as long as assessments are completed as part of standard of care and documentation of current certification is maintained in site Regulatory files.:
 - Questionnaire for Verifying Stroke-Free Status (QVSFS) If any question is answered "Yes," a formal neurologic examination and evaluation must be performed by a board-certified neurologist or clinical designee (e.g., neurology fellow).
 - NIH Stroke Scale (NIHSS).
 - Modified Rankin Scale (mRS) to establish the disability or dependence in the daily activities of people who have suffered a stroke or other causes of neurological disability at baseline.
- Current concomitant medications documentation.
- Adverse event assessment.

Prior to concluding the visit, research staff should also review the follow-up requirements with the subject to help ensure continued study compliance.

NOTE: Subjects who had a procedure attempt but did not receive an implant must be followed through the Primary Endpoints with a minimum of telehealth/phone call visits at all visits including 7-days, 45-days, 6-months, 12-months, and 18-months (imaging not required and protocol mandated medication therapy not required). After the 18-Month follow-up, these subjects will have completed all required study assessments.

9.13 Annual Follow-up 2 – 5 Years ± 60 Days Post Index Procedure (Telehealth)

All subjects will complete annual telehealth visits (at a minimum) at 2, 3, 4 and 5-years (± 60 days) post-index procedure to include the following assessments:

- Questionnaire for Verifying Stroke Free Status (QVSFS) If any question is answered "Yes," a formal neurologic examination and evaluation must be performed by a board-certified neurologist or clinical designee (e.g., neurology fellow).
- Current concomitant medications documentation.
- Adverse event assessment.

Prior to concluding the visit, research staff should also review the follow-up requirements with the subject to help ensure continued study compliance.

9.14 Suspected Stroke or Systemic Embolism Neurologic Events (Unscheduled Visit)

Subjects with confirmed stroke/TIA shall be followed in accordance with clinical standard of care until the neurologic event is completely resolved or resolved with stable deficit.

Subjects with a suspected TIA/stroke shall be documented as an Unscheduled Visit in the Electronic Database System, if identified at a timepoint that does not coincide with a scheduled follow-up visit. The requirements for a suspected TIA/stroke include the following assessments:

- Medical and Surgical History (documenting new findings on history since baseline assessment) and neurologic physical exam/assessment performed by a neurologist or clinical designee (e.g., neurology fellow).
- Physical Exam/Assessment

- A targeted neurologic assessment performed by a neurology professional (board-certified or board-eligible neurologist, neurology fellow, neurology physician assistant, or neurology nurse practitioner, or NIHSS- and/or mRS-certified staff where applicable), as long as assessments are completed as part of standard of care and documentation of current certification is maintained in site Regulatory files. Neurological assessment includes:
 - Questionnaire for Verifying Stroke-Free Status (QVSFS)
 - NIH Stroke Scale (NIHSS)

NOTE: the NIHSS should be evaluated in light of the subject's condition and should consider factors such as post-procedure anesthesia confusion and inability to raise leg due to constraints for other reasons such as hemostasis maintenance or underlying orthopedic limitations.

- Modified Rankin Scale (mRS) to establish the disability or dependence in the daily activities of people who have suffered a stroke or other causes of neurological disability at baseline.
- Brain Imaging as indicated based on clinical presentation; should include brain MRI/CT, in accordance with NeuroARC (29). CT imaging should only be used in cases where MRI (DW Imaging) is contraindicated. Brain Imaging is NOT required for subjects with Systemic Embolism (SE) without new findings suggestive of TIA/Stroke.
- TEE to evaluate LAAO implant (TEE required for subjects with confirmed TIA/Stroke or Systemic embolism).
- Current concomitant medications documentation.
- Adverse event assessment.
- In the event of a Stroke, 90 days following the event, documentation of a Neurologic evaluation including Modified Rankin Scale (mRS) is required. The Sponsor may request records (including imaging) related to this evaluation.
- In the event of a Systemic Embolism, 90 days following the event, documentation of a clinical evaluation is required. The Sponsor may request records (including imaging) related to this evaluation.

10 Study Completion

Subject participation in the study ends after the 5-year follow-up assessment, and the study completion form should be submitted at this time.

11 Protocol Deviations

All deviations from the requirements of this Clinical Investigation Plan will be considered protocol deviations. For any protocol deviation, a Protocol Deviation form should be completed in the eCRF indicating the type and reason for the deviation in accordance with FDA requirements outlined CFR 812.140 (a) (4), ISO 14155:2020, and other applicable regulations.

Protocol deviations include but are not limited to:

- Failure to obtain informed consent, or failure to obtain informed consent prior to the performance of study-specific procedures or assessments.
- Enrollment of a subject who did not meet all study inclusion criteria, or who met one or more study exclusion criteria.
- Failure to complete protocol-specified assessments, or completion of protocol-specified assessments outside of the protocol-defined time frame.

The Investigator shall not deviate from the protocol, however if a deviation from the protocol is deemed necessary by the Investigator to protect the safety or physical well-being of a subject, the Investigator is requested to notify the Sponsor as soon as possible (if possible, before the deviation has occurred) and IRB/REB/EC, if required.

The use of waivers in this clinical study protocol is prohibited unless approval is received in writing from the Sponsor or designee.

The Sponsor or its representatives will evaluate deviations to the clinical investigation plan during monitoring visits. Individual event corrective actions may be recommended at that time. In addition, deviations occurring across all investigational sites will be reviewed by the Sponsor or its representative on a periodic basis to determine if more global preventative actions may be required. The Sponsor may terminate an investigator or site's participation in the study (see Section 18.1.7).

Protocol deviations shall be reviewed and reported in the study reports, i.e., Annual Progress Report, as applicable.

12 Safety Reporting

Investigators are responsible for reporting and assessing all adverse events as applicable per protocol and all device deficiencies that could have led to a serious adverse device effect. These events will be documented in the case report forms for the study. In addition, the investigator is responsible for reporting any new and/or updated information related to already reported events. Adverse event collection for the study will occur from the time of randomization in the RCT cohort and at the time of consent for the Roll-In Cohort and Conscious Sedation Sub-Study Cohort.

In this study, subjects should also be encouraged to report adverse events (AEs) spontaneously or in response to general, non-directed questioning. During the study, the subject may volunteer information that resembles an adverse event (AE). If it is determined that an AE has occurred, the investigator should obtain all the information required to complete the AE CRFs.

12.1 Reportable Events by Investigational Sites

Investigators are responsible for reporting and assessing the following events:

- All serious adverse events
- All device and procedure-related adverse events
- UADE (Unanticipated Adverse Device Effects)/ USADE (Unanticipated Serious Adverse Device Effects)
- Pre-procedure events (e.g., events related to pre-procedure medication changes)
- All adverse events of special interest. The following events, regardless of seriousness or relatedness will be collected:

- Bleeding events
- Embolic events (e.g., stroke, TIA, systemic embolism)
- Neurologic events
- Device embolizations
- Device Related Thrombus
- Myocardial Infarction
- o Pericardial Effusion
- Vascular Complication

The following clinical events will not be considered reportable adverse events, unless the investigator considers the event to be related to the investigational device or procedure, or an AE of special interest:

- Pre-existing medical conditions or a repeat of symptoms are not required to be reported as adverse events *unless* there is a worsening in severity or frequency during a study.
- Planned procedures (scheduled prior to the index procedure) that occur after the index procedure are not considered reportable AEs. Complications from such procedures, however, must be reported.
- Abnormal non-cardiac laboratory findings are not considered a reportable AE unless:
 - The investigator determined that the finding is clinically significant, OR
 - The abnormal laboratory finding required intervention, OR
 - The abnormal laboratory finding required termination of the subject's participation in the study.

Investigators shall report relevant adverse events as follows:

- All sections of the Adverse Event CRF shall be completed for each applicable AE
- Each unique event/diagnosis must be documented separately
- Assess the relationship of the event to the investigational device and procedure
- The AE Term should be reported as a medical diagnosis if available, rather than clinical symptoms
- Death events should not be recorded as an adverse event, but as an outcome to a single serious adverse event
- The AE CRF must be reviewed and signed by the investigator
- If an AE is deemed not to be related to the device, procedure implant or medications and is not cardiovascular or neurological in nature AND; does not meet serious adverse criteria it does not need to be reported.

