13.2 Clinical Events Committee (CEC)

An independent Clinical Events Committee (CEC) will adjudicate all site-reported potential endpoint events and any other events the Sponsor deems necessary, in an ongoing fashion during the trial. Relationship of these events to the assigned device and/or procedure will also be adjudicated, and sub-classified as implant-related, delivery system-related or study medication related (anti-coagulation or antithrombotic) or related to a comorbid condition. The committee will include at least three voting members consisting of qualified physicians (cardiologists, interventional cardiologists, electrophysiologists and/or neurologist) experienced in clinical trials who are otherwise independent of the Sponsor and the conduct of the study. Members will also

be selected with consideration of their experience in the conduct of clinical trials and prior participation on a Clinical Events Committee.

Members will not have scientific, financial, or other conflicts of interest related to Conformal Medical, Inc. or the Investigator(s). The CEC will operate and conduct all meetings and event reviews independent of the Sponsor unless specific expert knowledge regarding the characteristics or function of the study device is requested by the CEC from the Sponsor.

The adjudication process, event definitions and required source document materials for each type of event will be pre-specified prior to the onset of the trial. The CEC members will review data collected from all relevant medical records, as well as all imaging study reports associated with an event to perform adjudication. All adjudication decisions will be made by the CEC in an independent and blinded fashion (to the extent possible) based upon review of all available medical evidence. Treatment assignment to investigational device/control device will be deidentified in any source documentation reviewed by the CEC to maintain blinding and reduce any potential bias.

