14.6 Additional Analyses

The following data will be summarized using descriptive statistics presented by treatment group in the ITT Randomized, Attempted, and Implanted populations, as applicable:

- Subject enrollment and data compliance by site and visit (data compliance at each visit is
 the percentage of subjects whose data forms have been collected and entered divided by
 the percentage of subjects whose forms should have been collected and entered).
- Frequency (number and percentage of subjects) with each type of concomitant medication.
- Frequency (number and percentage of subjects) with each site-reported Treatment Emergent AE overall and by MedDRA system organ class and preferred term (a treatment emergent AE is an AE that started or worsened during or after the index procedure).
- Frequency (number and percent of subjects) with each site-reported Treatment Emergent Serious AE overall and by MedDRA system organ class and preferred term.
- Frequency (number and percent of subjects) with each site-reported Treatment Emergent
 AE or SAE, by CEC-adjudicated relationship to the investigational device or procedure
 and CEC-adjudicated sub-classification as implant-related or delivery system-related.
- Protocol deviations (number and percentage of subjects with each deviation type).

Detailed listings on primary and secondary endpoints, site-reported AEs, and protocol deviations will be provided, as necessary.

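### Section 12.1 contains two reporting filters that disagree on non-serious medication-related events, non-serious cardiovascular events and unrelated bleeding

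*Protocol*

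**What the plan says.** Protocol Section 12.1 opens with "Investigators are responsible for reporting and assessing the following events" and lists five groups:

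- serious adverse events;
- "All device and procedure-related adverse events";
- UADE/USADEs;
- pre-procedure events, with medication changes before the procedure as the example;
- special-interest events, introduced by "All adverse events of special interest. The following events, regardless of seriousness or relatedness will be collected".

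The special-interest types are bleeding, embolic events, neurologic events, device embolization, device-related thrombus, myocardial infarction, pericardial effusion and vascular complication.

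A middle block then removes unchanged pre-existing conditions, planned procedures and certain laboratory findings. It restores them if they are device- or procedure-related or of special interest.

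The closing instructions tell sites: "Assess the relationship of the event to the investigational device and procedure". The last bullet is an exemption. It starts "If an AE is deemed not to be related to the device, procedure implant or medications and is not cardiovascular or neurological in nature" and adds that the event must not be serious; an event meeting all of these conditions need not be reported.

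Four other places bear on this:

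- Appendix A, under bleeding events, asks for every bleed to be reported whatever its BARC type.
- Section 14.10 says the CEC will adjudicate the cardiovascular adverse events that sites report, as a class, in addition to potential endpoint events.
- Section 13.2 has CEC-reviewed events "sub-classified as implant-related, delivery system-related or study medication related".
- Section 14.6 tabulates, by treatment group, the subjects "with each site-reported Treatment Emergent AE overall and by MedDRA system organ class and preferred term".

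**The concern.** A site needs one answer to whether a given non-serious event goes on a form. The opening list and the closing exemption draw the line in different places, and the protocol does not rank them. Two sites seeing the same arrhythmia, or the same drug reaction, could each follow Section 12.1 and differ on whether it is recorded. For bleeding, one part of the section orders collection and another waives it.

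The tables in Section 14.6 are built from what sites enter, so they inherit whichever filter each site applied. Bleeding complications are also a secondary safety endpoint (Section 8.5.3.1). A statistical analysis plan cannot repair this afterwards, because it cannot recover events that were never entered.

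**Working it through.** No sample size, error rate or event count is involved, so there is no figure to reproduce. The check applies both filters to each class of non-serious, post-procedure event.

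| Class (non-serious, post-procedure) | Opening list | Closing exemption | Result |
|---|---|---|---|
| a. Related only to medication, not special interest | not listed | not exempt | disagree |
| b. Unrelated cardiovascular, not special interest (e.g. arrhythmia, angina) | not listed | not exempt | disagree |
| c. Unrelated bleeding, neither cardiovascular nor neurological | must be collected | need not be reported | contradict |
| d. Device- or procedure-related | report | not exempt | agree |
| e. Neurologic event, myocardial infarction, pericardial effusion, medication-related bleeding | report | not exempt | agree |
| f. Unrelated, not cardiovascular or neurological, not special interest | not listed | exempt | agree |

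The filters part in 3 of 6 classes. That counts categories, not subjects or events.

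**Classes a and b.** Suppose the opening list were complete. A non-serious event unrelated to device and procedure and outside the special-interest types would then already be off the list, whether or not it was drug-related or cardiovascular. The medication and cardiovascular conditions in the last bullet would have no work to do. They make sense only if such events are meant to be reported. Section 14.10 points the same way: it presupposes that sites report cardiovascular events as a class, and the opening list has no such class.

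**Class c.** No inference is needed. The special-interest list applies whatever the seriousness or relatedness, and Appendix A repeats the requirement for all bleeding. The last bullet waives a bleed that is non-serious, judged unrelated, and neither cardiovascular nor neurological. The middle block of Section 12.1 carries an express exception for special-interest events; the last bullet carries none. In practice class c is limited to bleeds that a site judges unrelated to medication, since a medication-related bleed is not exempt.

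**Relatedness.** The last bullet turns on a judgement about medication, but the instruction to sites names only the investigational device and the procedure. It also does not name the control device, although the definitions in Section 12.2 and the relatedness categories in Appendix A include the comparator.

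**Reach.** The primary endpoint components (death, major bleeding, ischemic stroke, systemic embolism and the procedure-related complications) fall within the opening list. Major bleeding is BARC Type 3 to 5 and would ordinarily be serious, so the exemption would not remove it. Minor bleeding, Type 2, is where class c could affect the secondary endpoint.

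**The case against.** The best reply is that the last bullet is permissive. It says what may be left out and does not command reporting of everything else. The opening list can be read as the mandatory groups, with the bullet filtering what remains; a site that follows the list alone breaks no instruction in the bullet. This stands in part. For classes a and b the conflict rests on the natural reading of the bullet, not on a literal command. It does not answer class c, and it leaves open what a site should do with classes a and b.

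A reader might go further and infer three things that the documents do not support.

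- *That the comparison between arms is biased.* The trial is unblinded (Section 8.2.2) and the antithrombotic regimens are set separately for CLAAS and control (Sections 9.6.1 and 9.6.3), so reporting could differ by arm. But randomization is stratified by site, so one site's reading would ordinarily apply to both arms. Nothing shows sites switching rules by arm.
- *That safety data on DAPT alone, the subject of Objective 2, are lost.* Bleeding, embolic and neurologic events, device-related thrombus and myocardial infarction are collected as special-interest events. Reasons for interrupting or stopping DAPT are recorded at 7 days, 45 days and 6 months (Sections 9.8 to 9.10). What remains uncertain is non-serious drug effects outside the special-interest types that did not lead to interruption.
- *That the CEC's medication sub-classification contradicts the site instruction.* The CEC makes its own judgement from the medical records. The eCRF is not shown, so a missing medication field cannot be asserted.

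Two further limits hold. Pre-existing conditions that have not worsened are carved out, which matters for arrhythmia in patients with atrial fibrillation. After the 18-month visit, collection narrows to serious events, device deficiencies, unanticipated effects and special-interest events (end of Section 12.3), so classes a and b are in doubt only up to then.

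**Conclusion.** The point holds, as a defect in the reporting rule. Section 12.1 contains two filters that do not agree. They differ on non-serious events related only to antithrombotic medication and on non-serious unrelated cardiovascular events outside the special-interest types, taking the last bullet in its natural sense. They contradict each other outright on non-serious unrelated bleeding.

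The consequence is inconsistent capture across sites in the descriptive tables of Section 14.6, and possibly in the secondary bleeding endpoint. The primary hypothesis tests and the sample size are essentially untouched. No number of affected subjects and no difference between arms can be derived: either would need an incidence for these events and reporting rates by arm, and the documents give neither.

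**What to change.** Reconcile Section 12.1 into one rule that applies to both arms.

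1. Delete the last bullet, or make it expressly subject to the special-interest list as the middle block already is. This removes the contradiction on bleeding.
2. State in the opening list whether non-serious medication-related events and non-serious cardiovascular events are reportable. Section 14.10 favours including cardiovascular events. If the sponsor prefers the narrower scope, Section 14.10 should be reworded to match. Step 1 alone is not enough: deleting the bullet without this statement drops both classes silently.
3. Align the site relatedness instruction with the rule kept. Name the control device, as Section 12.2 and Appendix A do, and name medication if the rule depends on it.
4. Give the date from which the reconciled rule applies, so that the Section 14.6 tables can be read accordingly.

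The cost is a wording amendment, a memo to sites, and an eCRF relatedness field if none exists. With the broader scope, sites complete some additional non-serious event forms. Table 4 forecasts last enrollment for December 2026, so the change can still improve a good part of the follow-up.

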12.2 Safety Event Definitions

The definitions provided have references within the following regulations: 21 CFR Part 812, EU MDR 2017/745 and MDCG 2020-10/1.

Term	Definition
Adverse Event (AE)	An adverse event is any untoward medical occurrence, unintended disease or injury or untoward clinical signs (including an abnormal laboratory finding) in a subjects, users or other persons, whether or not related to the investigational medical device and whether anticipated or unanticipated.
	Note 1: This definition includes events related to the investigational medical device or the comparator Note 2: This definition includes events related to the procedures involved. Note 3: This includes 'comparator' if the comparator is a medical device.
Adverse Device Effect (ADE)	Adverse Event related to the use of an investigational medical device
	Note 1: This definition includes adverse events resulting from insufficient or inadequate instructions for use, deployment, implantation, installation, or operation, or any malfunction of the investigational medical device and/or delivery system.
	Note 2: This definition includes any event resulting from use error or from intentional misuse of the investigational medical device.
	Note 3: This includes ' comparator ' if the comparator is a medical device.
Serious Adverse Event (SAE)	Adverse Event that led to any of the following
	a) death,
	b) serious deterioration in the health of the subject, users, or other persons as defined by one or more of the following:
	1) a life-threatening illness or injury, or
	a permanent impairment of a body structure or a body function including chronic diseases, or
	3) in-patient or prolonged hospitalization, or
	4) medical or surgical intervention to prevent life- threatening illness or injury, or permanent impairment to a body structure or a body function
	c) fetal distress, fetal death, a congenital abnormality, or birth defect including physical or mental impairment
	Note 1: Planned hospitalization for a pre-existing condition, or a procedure required by the clinical investigational plan, without

	serious deterioration in health, is not considered a serious adverse event.
Serious Adverse Device Effect (SADE)	Adverse Device Effect that has resulted in any of the consequences characteristic of a serious adverse event.
Unanticipated Adverse Device Effect (UADE)	Any serious adverse effect on the health or safety or any life-threatening problem or death caused by, or associated with, a device, if that effect, problem, or death was not previously identified in nature, severity or degree of incidence in the investigational plan or application (including a supplementary plan or application), or any other unanticipated serious problem associated with a device that relates to the rights, safety or welfare of subjects.
	NOTE: An anticipated serious adverse device effect (ASADE) is a serious adverse device effect which by its nature, incidence, severity, or outcome has been identified in the investigational plan.
Unanticipated Serious Adverse Device Effect (USADE)	Serious Adverse Device Effect which by its nature, incidence, severity or outcome has not been identified in the current risk assessment
	Note 1: Anticipated serious adverse device effect (ASADE) is an effect which by its nature, incidence, severity or outcome has been identified in the risk assessment.
Serious Health Threat	Signal from any adverse event or device deficiency that indicates an imminent risk of death or a serious deterioration in the health in subjects, users or other persons, and that requires prompt remedial action for other subjects, users or other persons
	Note 1: This would include events that are of significant and unexpected nature such that they become alarming as a potential serious health hazard or possibility of multiple deaths occurring at short intervals.
Device Deficiency	Any inadequacy of a medical device with respect to its identity, quality, durability, reliability, usability, safety or performance.
	Note 1 : Device deficiencies include malfunctions , use errors , and inadequacy in the information supplied by the manufacturer including labelling.
	Note 2: This definition includes device deficiencies related to the investigational medical device or the comparator.

